### **Rescheduling**

Participants who require delay of treatment should be re-evaluated weekly or more frequently if clinically indicated and resume dosing when re-treatment criteria are met. Continue tumor assessments per protocol even if dosing is delayed.

### **Arm A:**

- Nivolumab may be delayed until the next planned ipilimumab dose if the next ipilimumab dose is scheduled within the next 12 days. This will permit periodic ipilimumab dosing to be synchronized with nivolumab dosing.
- Ipilimumab should be dosed at the specified interval regardless of any delays in intervening nivolumab doses. However, in order to maintain periodic synchronized dosing of ipilimumab and nivolumab, the dosing days of nivolumab and ipilimumab may be adjusted within the permitted  $\pm 2$  day window, as long as consecutive nivolumab doses are given at least 12 days

apart. Ipilimumab may be delayed beyond the 2-day window if needed to synchronize with the next nivolumab dose.

- If an ipilimumab dose is delayed beyond 6 weeks from the prior ipilimumab dose, then subsequent ipilimumab doses should be rescheduled to maintain the 6-week interval between consecutive ipilimumab doses.
- A dose delay of ipilimumab which results in no ipilimumab dosing for > 12 weeks requires ipilimumab discontinuation, with exceptions as noted in Section 4.5.5.

Arm B, C and D: Participants may be dosed no less than 12 days and 19 days from the previous treatment during Q2W (nivolumab) and Q3W (nivolumab combined with ipilimumab) dosing, respectively.

#### **4.5.4 Dose Reduction**

There will be no dose reductions for nivolumab or ipilimumab.

#### **4.5.5 Criteria to Resume Treatment**

Participants may resume study treatment when the drug-related AE(s) resolve(s) to Grade  $\leq$  1 or baseline, with the following exceptions:

- Participants may resume treatment in the presence of Grade 2 fatigue.
- Participants who have not experienced a Grade 3 drug-related skin AE may resume treatment in the presence of Grade 2 skin toxicity.
- For participants with Grade 2 AST, ALT and/or Total Bilirubin Abnormalities, dosing may resume when laboratory values return to baseline and management with corticosteroids, if needed, is complete. Participants with baseline Grade 1 AST/ALT or total bilirubin elevations who require dose delays for reasons other than a 2-grade shift in AST/ALT or total bilirubin may resume treatment in the presence of Grade 2 AST/ALT OR total bilirubin.
- Participants with isolated AST/ALT elevations or combined with total bilirubin elevations meeting discontinuation parameters ([Section 4.5.6](#)) should have treatment permanently discontinued, except situations outlined in the [Section 4.5.6](#).
- Drug-related pulmonary toxicity, diarrhea, or colitis must have resolved to baseline before treatment is resumed. Participants with persistent Grade 1 pneumonitis after completion of a steroid taper over at least 1 month may be eligible for retreatment if discussed with and approved by the BMS Medical Monitor.
- Drug-related endocrinopathies adequately controlled with only physiologic hormone replacement may resume treatment after consultation with the BMS Medical Monitor. If participant experienced Grade 3 adrenal insufficiency study treatment should not be resumed regardless of control with hormone replacement.

Participants with SARS-CoV-2 infection (either confirmed or suspected) may resume treatment after all of the following conditions are met:

- At least 10 days (20 days for severe/critical illness) have passed since symptoms first appeared or positive test result (eg, reverse transcription polymerase chain reaction or viral antigen)
- Resolution of acute symptoms (including at least 24 hours has passed since last fever without fever reducing medications)
- Evaluation by the investigator with confirmation that there are no sequelae that would place the participant at a higher risk of receiving investigational treatment.

For suspected cases, treatment may also resume if SARS-CoV-2 infection is ruled out and other criteria to resume treatment are met.

Prior to re-initiating treatment in a participant with a dosing delay lasting > 8 weeks, the Medical Monitor (or designee) must be consulted. Continue tumor assessments per protocol even if dosing is delayed. Continue periodic study visits to assess safety and laboratory studies every 8 weeks or more frequently if clinically indicated during such dosing delays.

When criteria to resume treatment are met, resume both nivolumab and ipilimumab on the same day unless the investigator determines that 1 of the agents must be discontinued due to toxicity attributed to that agent alone.

#### **4.5.6 Treatment Discontinuation Criteria**

Treatment should be permanently discontinued for any of the following:

- Any Grade 2 drug-related uveitis or eye pain or blurred vision that does not respond to topical therapy and does not improve to Grade 1 severity within the re-treatment period OR requires systemic treatment
- Any Grade 3 non-skin, drug-related AE lasting > 7 days, with the following exceptions for drug-related uveitis, pneumonitis, bronchospasm, hypersensitivity reactions, infusion reactions, endocrinopathies, diarrhea, colitis, neurologic toxicity and laboratory abnormalities:
  - Grade 3 drug-related uveitis, pneumonitis, bronchospasm, diarrhea, colitis, myocarditis, neurologic toxicity, hypersensitivity reaction, or infusion reaction of any duration requires discontinuation. Grade 3 drug-related endocrinopathies adequately controlled with only physiologic hormone replacement do not require discontinuation. Grade 3 adrenal insufficiency requires discontinuation regardless of control with hormone replacement.
    - ◆ Grade 3 drug-related laboratory abnormalities do not require treatment discontinuation except:
      - Grade 3 drug-related thrombocytopenia > 7 days or associated with bleeding requires discontinuation.
      - Grade  $\geq 3$  drug-related AST, ALT or Total Bilirubin requires discontinuation\*
      - Concurrent AST or ALT  $> 3 \times$  ULN and total bilirubin  $> 2 \times$  ULN\*
  - \*In most cases of Grade 3 AST or ALT elevation, study drug(s) will be permanently discontinued. If the investigator determines a possible favorable benefit/risk ratio that warrants continuation of study drug(s), a discussion between the investigator and the BMS Medical Monitor/designee must occur.

- Any Grade 4 drug-related adverse event or laboratory abnormality, except for the following events, which do not require discontinuation:
  - Grade 4 neutropenia  $\leq$  7 days
  - Grade 4 lymphopenia or leukopenia
  - Isolated Grade 4 amylase or lipase abnormalities that are not associated with symptoms or clinical manifestations of pancreatitis. The BMS Medical Monitor should be consulted for Grade 4 amylase or lipase abnormalities
  - Isolated Grade 4 electrolyte imbalances/abnormalities that are not associated with clinical sequelae and are corrected with supplementation/appropriate management within 72 hours of their onset
  - Grade 4 drug-related endocrinopathy adverse events such as hyper- or hypothyroidism, or glucose intolerance, which resolve or are adequately controlled with physiologic hormone replacement (corticosteroids, thyroid hormones) or glucose controlling agents, respectively, may not require discontinuation after discussion with and approval from the BMS Medical Monitor
- Dosing delays lasting  $>$  6 weeks for Q2W dosing (nivolumab monotherapy) or  $>$  8 weeks for Q3W dosing (nivolumab combined with ipilimumab) from the previous dose requires discontinuation. The following exceptions apply:
  - Dosing delays to allow for prolonged steroid tapers to manage drug-related adverse events are allowed.
  - Dosing delays lasting  $>$  6 weeks from the previous dose that occur for non-drug-related reasons may be allowed if approved by the BMS medical monitor.
- Any adverse event, laboratory abnormality, or intercurrent illness which, in the judgment of the Investigator, presents a substantial clinical risk to the participant with continued nivolumab dosing.

Prior to re-initiating treatment in a participant with a dosing delay lasting  $>$  6 weeks, the BMS medical monitor must be consulted. Tumor assessments should continue as per protocol even if dosing is delayed. Periodic study visits to assess safety and laboratory studies should also continue every 6 weeks or more frequently if clinically indicated during such dosing delays.

The assessment for discontinuation of ipilimumab should be made separately from the assessment made for discontinuation of nivolumab. Although there is an overlap among the discontinuation criteria, if discontinuation criteria are met for ipilimumab but not for nivolumab, treatment with nivolumab may continue if ipilimumab is discontinued.

If a participant meets the criteria for discontinuation of ipilimumab but not nivolumab, treatment with nivolumab may not resume until the AE/SAE has fully resolved and the participant has discontinued steroids, if they were required for treatment of the AE/SAE. The relationship to ipilimumab should be well documented in the source documents. Nivolumab should be resumed at the dose according to the treatment schedule ([Table 5.1-2](#), [Table 5.1-3](#) and [Table 5.1-4](#)).

Participants receiving nivolumab plus ipilimumab treatment arm, who meet criteria for treatment discontinuation and an investigator is unable to determine whether the event is related to both or one study drug, the participant should discontinue both nivolumab and ipilimumab and be taken off the treatment phase of the study.

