## **3.4          *Concomitant Treatments***

### **3.4.1       *Prohibited and/or Restricted Treatments***

The following medications and treatments are prohibited during the study (unless utilized to treat a drug-related adverse event):

- Immunosuppressive agents
- Immunosuppressive doses of systemic corticosteroids. Participants are permitted the use of topical, ocular, intra-articular, intranasal, and inhalational corticosteroids (with minimal systemic absorption). Adrenal replacement steroid doses  $> 10$  mg daily prednisone are permitted. A brief (less than 3 weeks) course of corticosteroids for prophylaxis (eg, contrast dye allergy) or for treatment of non-autoimmune conditions (eg, delayed-type hypersensitivity reaction caused by a contact allergen) is permitted.
- Any concurrent systemic anti-neoplastic therapy (ie, chemotherapy, hormonal therapy, immunotherapy, or standard or investigational agents for treatment of CRC)
- Any non-palliative radiation therapy. Radiation therapy administered with palliative intent (ie, for pain, bleeding, spinal cord compression, brain metastasis, new or impending pathologic fracture, superior vena-cava syndrome, or obstruction) is permitted.
- Any complementary medications (eg, herbal supplements or traditional Chinese medicines) intended to treat the disease under study. Such medications are permitted if they are used as supportive care.
- Any live / attenuated vaccine (eg, varicella; zoster; yellow fever; rotavirus; oral polio; and measles, mumps, rubella) during treatment and until 100 days post last dose.
  - COVID-19 vaccines that are NOT live are allowed and should be handled in the same manner as other vaccines. Administration may occur during the study, including during the administration of the BMS study treatment and after the last administration of the BMS study treatment. Non-live COVID-19 vaccination is considered a simple concomitant medication within the study. However, the efficacy and safety of non-live vaccines (including non-live COVID-19 vaccines) in participants receiving nivolumab and/or ipilimumab are unknown.

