### **3.5 Discontinuation of Participants following any Treatment with Study Drug**

Participants MUST discontinue investigational product (and non-investigational product at the discretion of the investigator) for any of the following reasons:

- Participant's request to stop study treatment and/or participation in the study
- Any clinical AE, laboratory abnormality, or intercurrent illness which, in the opinion of the investigator, indicates that continued participation in the study is not in the best interest of the participant
- Pregnancy\*
- Termination of the study by BMS
- Loss of ability to freely provide consent through imprisonment or involuntarily incarceration for treatment of either a psychiatric or physical (eg, infectious disease) illness
- Inability to comply with protocol
- Documented disease progression (or documentation of further progression for participants receiving treatment beyond progression; see [Section 4.5.7](#)). Participants without documented disease progression can discontinue study treatment if they have investigator assessed clinical deterioration that is unstable to perform further tumor assessment, and it should be well documented).
- Any AE meeting discontinuation criteria (see [Section 4.5.6](#)).

\* In the case of pregnancy, the investigator must immediately notify the BMS Medical Monitor/designee of this event. In most cases, the study drug will be permanently discontinued in an appropriate manner. If the investigator determines a possible favorable benefit/risk ratio that warrants continuation of study drug, a discussion between the investigator and the BMS Medical Monitor/designee must occur

All participants who discontinue investigational product should comply with protocol specified follow-up procedures as outlined in [Section 5](#). The only exception to this requirement is when a participant withdraws consent for all study procedures including post-treatment study follow-up or loses the ability to consent freely (ie, is imprisoned or involuntarily incarcerated for the treatment of either a psychiatric or physical illness).

If study drug is discontinued prior to the participant's completion of the study, the reason for the discontinuation must be documented in the participant's medical records and entered on the appropriate case report form (CRF) page.

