##### **4.5.3 Dose Delay Criteria**

Study treatment should be delayed for the following:

- Any Grade  $\geq$  2 non-skin, drug-related AE, except for fatigue
- Grade 2 drug-related creatinine, AST, ALT, and/or Total Bilirubin Abnormalities, with the following exceptions:

- If a participant has baseline AST, ALT, or total bilirubin within the Grade 1 toxicity range, delay dosing for drug-related Grade  $\geq 3$  toxicity
- See [Section 4.5.6](#) for discontinuation criteria for drug-related ALT, AST and/or Total Bilirubin Abnormalities
- Any Grade  $\geq 3$  skin drug-related AE
- Any Grade 3 drug-related laboratory abnormality with the following exceptions:
  - Grade 3 lymphopenia or asymptomatic amylase or lipase does not require a dose delay
- Any AE, laboratory abnormality or inter-current illness which, in the judgment of the investigator, warrants delaying the dose of study medication.

Dosing of nivolumab and ipilimumab should be delayed for any adverse event, laboratory abnormality, or intercurrent illness which, in the judgment of the investigator, warrants delaying the dose of study medication. Study therapy should also be delayed in cases of confirmed or suspected severe acute respiratory syndrome coronavirus 2 (SARS-CoV-2) infection regardless of the severity.

Participants receiving nivolumab in combination with ipilimumab who have drug-related toxicities that meet the criteria for dose delay should have both drugs (nivolumab and ipilimumab) delayed until treatment resumption criteria are met.

Participants who require delay of nivolumab and/or ipilimumab should be re-evaluated weekly or more frequently if clinically indicated and resume nivolumab and/or ipilimumab dosing when retreatment criteria are met.

Dose delay criteria apply for all drug-related adverse events regardless of whether the event is attributed to nivolumab or ipilimumab or both.

Doses of nivolumab or ipilimumab may be interrupted, delayed, or discontinued depending on how well the participant tolerates the treatment. Dosing visits are not skipped, only delayed.

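### The Grade 4 endocrinopathy exception in Section 4.5.6 can be read to keep controlled Grade 4 adrenal insufficiency on drug, although Grade 3 must stop regardless of control

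*Combined protocol and SAP*

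**What the plan says.** Protocol Section 4.5.6 lets Grade 3 endocrinopathies continue if physiologic replacement controls them, then carves out one condition: "Grade 3 adrenal insufficiency requires discontinuation regardless of control with hormone replacement". Section 4.5.5 matches this for re-dosing: "If participant experienced Grade 3 adrenal insufficiency study treatment should not be resumed regardless of control with hormone replacement".

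At Grade 4, Section 4.5.6 requires discontinuation for any drug-related event except those listed. One listed exception covers Grade 4 endocrinopathies, with hyper- or hypothyroidism and glucose intolerance as examples. Where these resolve or are controlled with "physiologic hormone replacement (corticosteroids, thyroid hormones) or glucose controlling agents, respectively, may not require discontinuation after discussion with and approval" from the Medical Monitor, treatment may go on.

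The neighbouring rules are:

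- Section 4.5.3 delays dosing for any Grade 2 or higher "non-skin, drug-related AE, except for fatigue", so re-dosing goes through Section 4.5.5.
- Section 4.5.5 has a general sentence with no grade limit: "Drug-related endocrinopathies adequately controlled with only physiologic hormone replacement may resume treatment after consultation with the BMS Medical Monitor".
- Section 3.4.1 opens one permission with "Adrenal replacement steroid doses" and allows them above 10 mg daily prednisone during the study.
- Investigator-judgment stops remain. Section 4.5.6 has one for any event that "presents a substantial clinical risk to the participant with continued nivolumab dosing"; Section 3.5 has one where, in the investigator's opinion, the event "indicates that continued participation in the study is not in the best interest of the participant".

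**The concern.** A stopping rule should not become more permissive as the event becomes more severe. Read literally, controlled Grade 2 adrenal insufficiency may resume after consultation, Grade 3 may never resume, and controlled Grade 4 may continue if the Medical Monitor approves. A site that reads the Grade 3 rule as covering Grade 4 would stop. A site that relies on the exception could ask for approval and, if it is given, re-expose a participant whose milder counterpart must stop. The matter is one of participant safety and consistent conduct. It does not touch the response-rate analysis or any other endpoint.

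**Working it through.** The plan states no figure to reproduce, so the check is a comparison of the rules by grade, followed by date arithmetic for the size of the exposed group.

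**Rules for adrenal insufficiency controlled on physiologic replacement**

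| Grade | Discontinuation (4.5.6) | Resumption (4.5.5) |
|---|---|---|
| 2 | Not a named stop | Allowed after Medical Monitor consultation |
| 3 | Mandatory stop | Barred |
| 4, literal reading | Default stop, lifted by the endocrinopathy exception if the Medical Monitor approves | General sentence has no grade limit; the only adrenal bar names Grade 3 |
| 4, stricter reading | Stop, because Grade 4 exceeds Grade 3 | Barred, because the participant counts as having had Grade 3 |

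Three features of the text make the literal reading reasonable:

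1. The conditions in the exception are introduced by *such as*, so the list is open. Adrenal insufficiency is neither named nor excluded.
2. The exception names corticosteroids as hormone replacement. They replace no hormone in the thyroid or glucose examples, so the word points to steroid-replaced endocrinopathies, the group that includes adrenal insufficiency.
3. The protocol writes Grade ≥ 3 when it means that: for AST, ALT and bilirubin in Section 4.5.6 and for skin events in Section 4.5.3.

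Other Grade 3 stops in Section 4.5.6, such as pneumonitis, colitis and myocarditis, also name Grade 3 only. They are safe because the Grade 4 default catches them and no Grade 4 exception reaches them. Adrenal insufficiency differs because an exception can reach it.

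No other readable section states a rule for Grade 4 or Grade ≥ 3 adrenal insufficiency. The delay rule in 4.5.3 only sends the case to 4.5.5, and Section 3.4.1 does not bar replacement steroids. The requirement in 4.5.6 to be off steroids before nivolumab resumes applies only when ipilimumab's discontinuation criteria are met and nivolumab's are not.

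**Size of the exposed group**

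Inputs: Part 2 enrollment closed on 20-Dec-2021 with 9 participants treated in Arm D (Section 3.1.1); four ipilimumab doses at 3-week intervals; a 24-month cap, or up to 12 months after onset of a second-year response (Section 3.1.1); Amendment 07 dated 22-Aug-2022 (Document History).

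- Last undelayed ipilimumab dose for the latest possible starter: 20-Dec-2021 + 3 × 21 days = 20-Dec-2021 + 63 days = 21-Feb-2022. That is 182 days before Amendment 07, so later exposure is ordinarily nivolumab alone.
- 24-month cap: 20-Dec-2023, which is 485 days after Amendment 07.
- Latest late responder: 24 + 12 = 36 months, so 20-Dec-2024, which is 851 days after Amendment 07.
- Part 1: dosing dates are not given. Assuming every Part 1 participant had started by 08-Apr-2019, when Part 2 was added, the 36-month maximum ends on 08-Apr-2022, 136 days before Amendment 07. The ceiling is then the 9 Arm D participants. Any later Part 1 starter still on drug would add to it.

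**The case against.** The best counter-argument is structural. Section 4.5.6 requires discontinuation if any one bullet is met, and the exception sits under the Grade 4 bullet, so it lifts that bullet only and leaves the separate adrenal insufficiency stop standing. Section 4.5.5 asks what the participant has experienced, and someone who reached Grade 4 has plausibly reached Grade 3 too. A specific stop would ordinarily prevail over a general permission whose examples do not include the condition. This reading is plausible and may well be what the sponsor intends. It is not written down, however: the adrenal stop is placed under the Grade 3 bullet and names Grade 3 only. If it is the intent, the edit merely records it.

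Second, nobody continues automatically. Control and Medical Monitor approval are both required, a site that does not ask defaults to stopping, and the investigator-judgment stops remain. This stands, and it limits how far sites could diverge. It still leaves to discretion at Grade 4 what the protocol takes out of discretion at Grade 3.

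Third, the Appendix 3 endocrinopathy algorithm is a figure that is not shown, and Section 4.5.8 says the algorithms are also in the Investigator Brochures. These could not be checked. Appendix 3 describes itself as guidance, so this lowers confidence without settling the point.

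Fourth, enrollment is closed, few people are exposed, and Grade 4 adrenal insufficiency would have to occur and be controlled before the question arises. That bears on how often the gap would matter, not on whether the rule is sound.

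**Conclusion.** The concern holds as a statement about the visible text: Section 4.5.6 can be read to let controlled Grade 4 adrenal insufficiency continue with approval, while Grade 3 must stop regardless of control. Confidence is medium, because this is an inference from an open list and a stricter reading is available. The documents give no rate of adrenal insufficiency, so the number of affected participants cannot be estimated. The 9 people and the 485- and 851-day windows are ceilings on exposure; they rest on first dosing no later than the closure date and, for the 9, on the Part 1 assumption above. The correction should be made because it concerns a stopping rule and is inexpensive.

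**What to change.** Make three short edits:

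1. In the adrenal insufficiency sentence of Section 4.5.6, change Grade 3 to *Grade ≥ 3*.
2. Make the same change in the adrenal insufficiency sentence of Section 4.5.5.
3. In the Grade 4 endocrinopathy exception of Section 4.5.6, add *except adrenal insufficiency*. Keep corticosteroids in the text for other steroid-replaced endocrinopathies.

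Controlled Grade 4 adrenal insufficiency then requires discontinuation, as Grade 3 does. No new data or procedures are needed. Section 9.1.1 does mention revision by administrative letter, but because a stopping rule changes, an amendment with IRB/IEC approval is the appropriate route; the practical course is to include the edits in the next amendment. The cost is that the Medical Monitor loses discretion to continue a participant with controlled Grade 4 adrenal insufficiency, a discretion the protocol already withholds at Grade 3.
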